9.2 Randomization

Randomization is carried out as central fax randomization. The randomization form (appendix 3) has to be faxed to the following address:

Clinical Study Core Unit, SZB
Institute of Clinical Chemistry and Chlinical Pharmacology
University of Bonn

[contact]

Phone (in case of any problems): [name]

Randomization is carried out according to a predefined randomization list for each center provided by the Institut für Medizinische Biometrie, Informatik und Epidemiologie (IMBIE), University of Bonn. Due to the different schedules for application of CCNU/TMZ (6 week courses) and standard TMZ (4-week courses), blinding of patients and of the treating physician is not possible. However, the reference neuroradiologist determining the day of progression on MRI will be blinded to the treatment protocol.

Randomization is stratified per participating center. Since age (<50 vs. ≥50 years), performance score (WHO performance score 0 vs. 1 or 2), extent of surgery (complete or partial resection vs. biopsy only) and mental state (MMSE ≥27 vs. <27) are strong prognostic factors in patients with newly diagnosed GBM (Gorlia et al., 2008), it would be desirable to also stratify randomization according to these parameters. With an average number of 10 patients recruited per center this does not appear to be feasible. Therefore, randomization is only stratified by center and the other prognostic factors are taken into account in the prespecified data analysis. The above mentioned prognostic factors have been implemented in 3 prognostic classes of GBM patients that have been developed by recursive partitioning analysis (RPA, Curran et al., 1993), validated in further trials (Scott et al., 1998) and further modified and validated using the data of the EORTC/NCIC trial (Mirmanoff et al., 2006) which defines the standard arm of CeTeG. The confirmatory analysis of the CeTeG trial will therefore analyze the primary endpoint OS not only stratified by center but also stratified by RPA class.

9.3 Statistical and Analytical Methods: Efficacy parameters

Statistical analysis starts 36 months after the inclusion of the last patient. Statistical analysis will be performed at the Institute of Medical Biometry, Informatics and Epidemiology (IMBIE) at the University of Bonn Medical Center (Dir.: [name]. [name]). OS, the primary parameter, will be compared between treatment groups using a two-sided log-rank-test at a level of 5% stratified for center and for RPA class. Centers contributing less than 3 patients for one arm of the treatment arms are pooled in this analysis. The primary confirmatory analysis will be based on the intention-to-treat (ITT) population. The ITT population contains all patients who have received a first dose

of chemotherapy (CCNU in the experimental arm and TMZ in the standard arm). Dropouts will be evaluated as censored observations at the time of dropout. An additional comparison will be made based on the per protocol population. The results of both analyses should be consistent. The per-protocol analysis includes all patients who have received two courses of CCNU/TMZ in the experimental arm or concomitant TMZ plus one course of adjuvant TMZ in the standard arm. Additionally, an analysis of the “as randomized” population will be performed.

The following secondary efficacy endpoints are also determined:

- Progression-free survival (PFS) determined by MRI (modified RANO criteria)
- Best response rate determined by MRI (modified RANO criteria)
- Frequency of delay of the next CCNU/TMZ or TMZ course by more than 2 weeks
- Acute toxicity during radiotherapy and chemotherapy according to CTC AE V4.0
- Quality of life, determined by EORTC QLQ questionnaires
- Evaluation of late neurotoxicity by MMSE and NOA-07 test battery

Survival parameters are measured in days starting from the day of start of treatment (first day of RT). Surviving patients and patients lost for follow-up are censored for the Kaplan-Meier analysis. Overall survival and progression-free survival will be summarized by Kaplan-Meier curves. Median time estimates as well as associated 95% confidence intervals will be reported. In addition Cox regression analyses adjusted and unadjusted for stratification factors such as age, performance score, extent of resection will be performed in an exploratory manner. The analysis will be based on the intent-to-treat population and repeated for the per-protocol population.

A plan for the complete analysis of the collected data will be developed before the end of the data collection. All additional analyses such as subgroup analyses (PFS and OS according to resection status) will be purely descriptive.

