Study Design / Development phase	Prospective, open-label, randomized, multicenter phase III study
Objective	To analyze whether combined CCNU/TMZ therapy is superior to standard TMZ regarding efficacy as measured by overall survival
Number of subjects	To be assessed for eligibility n = 658 To be allocated to trial n = 141 To be analyzed n = 128 (ITT)
Investigational products	TMZ (Temozolomide) CCNU (Lomustine)
Treatment plan	After central neuropathology confirmation of glioblastoma and confirmation of a methylated MGMT status, patients are randomized into 2 arms: Experimental arm (CCNU/TMZ arm): 60 Gy standard radiotherapy (RT, 30 x 2 Gy) Six 42-day courses of oral CCNU 100 mg/m ² (day 1) and oral TMZ 100 mg/m ² (day 2-6), first CCNU application starting with the first day of RT CCNU/TMZ and radiotherapy start 2-5 weeks after diagnosis (day of surgery for glioblastoma (GBM)). In courses 2-6, TMZ dose are adjusted according to the hematotoxicity observed in the previous course and can be increased stepwise

	
up to 200 mg/m²/day
 
Standard arm (TMZ arm): 60 Gy standard radiotherapy (RT, 30 x 2 Gy) and concomitant TMZ therapy (daily TMZ 75 mg/m²) starting with the first day of radiotherapy Six 28-day courses of TMZ (day 1-5) starting 4 weeks after completion of radiotherapy. In the first course TMZ is given at a dose of 150 mg/m²/day, in case no toxicity is observed, the 2nd course is applied at a daily dose of 200 mg/m² Concomitant TMZ and radiotherapy start 2-5 weeks after diagnosis
 
Follow-up per patient: Each patient will be followed until at least 36 months after randomization. Follow-up of all patients ends 36 months after the inclusion of the last patient. All patients in the trial are followed until this time point.
 
Duration of intervention per patient: Experimental arm: 6 courses CCNU/TMZ à 42 days = 9 months Standard arm: 6 weeks radiotherapy + concomitant TMZ, 4 weeks treatment pause, 6 courses of TMZ à 28 days = 8.5 months

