
Discontinuation rules
	
Discontinuation of the whole trial
 
 • The trial will be stopped in case of unacceptable toxicity. Unacceptable toxicity is found if more than 2 of the first 30 patients in one of the arms of the trial die from acute complications of therapy. • Additionally, the DMSB and/or the coordinating investigator as the designee of the sponsor can stop the trial transiently or permanently for any safety reason. • There is no interim analysis for efficacy. Thus there is no stopping rule based on efficacy parameters. 
Discontinuation rules for an individual patient. An individual patient will be discontinued from study therapy under the following circumstances:
 
 • There is MRI- defined progressive disease according to modified RANO criteria. • The patient requests discontinuation (as long as the patient consents explicitly for further follow-up): 
 ▪ Non-compliance of the patient • The drugs exhibit unacceptable toxicity: 
 Delay of the next course for 6 weeks or more due to hematological toxicity Any non-hematological CTCAE grade 3/4 toxicity attributable to CCNU or temozolomide. Those patients may receive temozolomide or CCNU monotherapy, respectively, if toxicity can be clearly attributed to one of the the agents • The patient becomes pregnant

Statistical analysis
	
Efficacy: Overall survival (OS) as primary efficacy parameter is measured from the day of randomization into one of the study arms until death. OS will be compared between the two treatment groups using a two-sided log-rank test at a level of 5% stratified for center and GBM recursive partitioning analysis (RPA) class.
 
Description of the primary efficacy analysis and population: The primary analysis will be performed according to the intention to treat (ITT) principle. The intent-to treat (ITT) analysis includes all 128 patients who have been randomized in the trial and have started with the first dose of CCNU (experimental arm) or TMZ

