	
(standard arm). Dropouts will be evaluated as censored observations at the time of dropout. An additional per-protocol analysis includes all patients who have received two courses of CCNU/TMZ (experimental arm) or concomitant TMZ plus one course of adjuvant TMZ (standard arm). The results of both tests are expected to be consistent. Additionally, an analysis of the “as randomized” population will be performed.
 
Safety: All patients randomized in the trial will be evaluated for safety. Adverse events are recorded by a standardized questionnaire for each course of chemotherapy. Long-term safety will be also evaluated by determining the rate of late neurotoxic sequelae through repeated neurocognitive testing using the NOA-07 test battery and repeated MRI.
 
Secondary endpoints: Secondary endpoints are overall survival, response rate, rate of delay of the next CCNU/TMZ or TMZ course and quality of life/neurocognitive functioning. These parameters are analyzed for the ITT and the per protocol population

--	---

ABBREVIATIONS

AE	Adverse event
AP	Alkaline phosphatase
ALAT	Alanine transaminase
ANC	Absolute neutrophil count
ASAT	Aspartate transaminase
BfArM	Bundesinstitut für Arzneimittel und Medizinprodukte
CCNU	Lomustine
CBC	Complete blood count
CR	Complete response
CRF	Case report form
CT	Computed tomography
CTC	Common toxicity criteria
CTCAE	Common Terminology Criteria for Adverse Events
DNA	Deoxyribonucleic acid
EDC	Electronic Data Capture
EORTC	European Organization for Research and Treatment of Cancer Quality of Life
GBM	Glioblastoma
GCP	Good clinical practice
ICH	International Conference on Harmonization
Investigator	A person responsible for the conduct of the clinical trial at a designated study center
ITT	Intention to treat
KPS	Karnofsky Performance Status
MGMT	O6-methylguanin-DNA-methyltransferase
mMGMT	methylated MGMT promoter
mPFS	Median progression-free survival
nmMGMT	non-methylated MGMT promoter
MMST	Mini Mental Status Test
MRI	Magnetic resonance imaging

NCI	National Cancer Institute
OS	Overall survival
PD	Progressive disease
PCV	Procarbazine, CCNU, Vincristine
PFS	Progression-free survival
PI	Principal investigator
PR	Partial response
QoL	Quality of life
SAE	Serious Adverse Event
SD	Stable disease
SOP	standard operational procedures
TMZ	Temozolomide
TTP	Time to progression
ULN	Upper limit of normal range
WBC	White blood cell

INVESTIGATOR AGREEMENT

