The assumptions for the initial planning of the trial match to event (death) rates of 0.356 and 0.176 events per patient year and result in an expected number of 68 events after two years of recruitment and two years of follow-up. . A blinded analysis of the overall survival time 14 months after last-patient-in (36 months after first-patient-in) showed that there is an overall mean risk for the event “death” of 0.1994/patient year due to an unexpected low number of events at this time and indicating a low number of events at the end of the intended follow-up-time which might result in a power lower as expected. With the observed actual event rate and an assumed OR of 2 as planned, the 68 events required for an analysis with a sufficient power of 80% can be reached by a prolongation of the follow-up time to April 2017, i.e. 36 months after last-patient-in. The sample size calculation was performed using the “PS” power and sample size program (Dupont and Plummer, 1997) and additional simulation analysis. Assuming that 6% of patients may not be analyzable for the primary endpoint OS due to non-compliance or loss to follow-up before the start of chemotherapy, additional 8 patients adding up to a total of 136 MGMT-methylated patients have to be randomized for the trial. Dropout patients and patients lost for follow-up after the start of chemotherapy will be evaluated as observations censored at the time of dropout. The figure of approx. 6% patients who may be non-compliant and/or lost for follow-up for the ITT evaluation of the primary endpoint may be overestimated. In the previous bicentric phase II trial with CCNU/TMZ ([name] et al., 2006; Glas et al., 2009), none of the 31 patients included was lost for follow-up or non-compliant. This corresponds to experiences of most centers with other trials for untreated GBM such as the so far not published phase II cilengitide trial. In experienced neurooncological centers as the ones taking part in the CeTeG trial, the lost-to-follow-up rate is very low. The long-term analysis of the EORTC/NCIC trial

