9.4 Safety Analysis

Patients who did not receive at least one dose of any study medication will be excluded from the analysis of safety. Tables of adverse event incidence (preferred term classification) and individual incidence will be produced. A complementary analysis of adverse events by severity of event and by relationship to trial treatment will also be performed. Dose reductions, delay of therapy in subsequent courses ("Frequency of

delay of the next CCNU/TMZ or TMZ course by more than 2 weeks” as secondary endpoint) and premature withdrawals will also be described.

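### The confirmatory survival set called ITT is a treated-patient set: randomized patients who never start chemotherapy are left out

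*Protocol*

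**What the plan says.** - **Confirmatory set.** Section 9.3: "The primary confirmatory analysis will be based on the intention-to-treat (ITT) population". It then defines that set: "The ITT population contains all patients who have received a first dose" of chemotherapy. The qualifying drug is CCNU in the experimental arm and TMZ in the standard arm. The synopsis (Statistical analysis) agrees: "The intent-to treat (ITT) analysis includes all 128 patients who have been randomized in the trial and have started with the first dose of CCNU" or, in the standard arm, of TMZ.
- **Expected exclusions.** Section 3.6 has 136 patients allocated, 128 in the ITT set, and 8 (about 6%) dropping out before chemotherapy without replacement. Section 9.1 gives the reason: "6% of patients may not be analyzable for the primary endpoint OS due to non-compliance or loss to follow-up before the start of chemotherapy". It adds that 6% may be too high, citing 0 of 31 in the earlier phase II trial and 9 of 573 (1.6%) who refused further involvement in the trial that set the standard arm.
- **Knowledge of the arm.** Section 9.2 says that patients and treating physicians cannot be blinded. Section 4 lets therapy start up to 2 weeks after randomization.
- **All-randomized analysis.** The synopsis and 9.3 plan an as-randomized analysis in addition to the ITT and per-protocol ones, with no confirmatory role.
- **Time origin and censoring.** Sections 2.3 and 6.2.2 run OS from randomization to death, in 6.2.2 from any cause. Section 9.3 measures survival from the first day of radiotherapy and censors dropouts at the time of dropout.
- **Related mismatches.** Safety set: "All patients randomized in the trial will be evaluated for safety" (synopsis) against "Patients who did not receive at least one dose of any study medication will be excluded from the analysis of safety" (9.4). Number allocated: "To be allocated to trial n = 141" (synopsis) against 136 in 3.6 and 9.1.

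**The concern.** Randomization makes the arms comparable as allocated. It gives no such guarantee for a subset formed afterwards by an event that can depend on the arm. Starting chemotherapy is such an event here, because patient and physician know the allocation before the first dose. The protocol itself expects more myelotoxicity with the combination (1.1, 1.3, 11), so refusal after allocation could differ by arm. Patients disappointed at drawing the standard arm could also leave, which would act in the opposite direction.

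The entry condition also differs by arm. Read literally, a patient allocated to the combination who never takes CCNU but takes TMZ leaves the set, while a patient allocated to TMZ who takes TMZ stays.

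The trial's single confirmatory test is at stake. Its p-value would come from a set selected after allocation was known, and the report would call it intention-to-treat.

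**Working it through.** **1. Reproduce the plan's figures.** Inputs (9.1): 2-year survival 48.9% and 70%, exponential survival, 64 per arm, 2 years of accrual, and originally 2 years of follow-up.

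- Hazards: −ln(0.489)/2 = 0.358 and −ln(0.70)/2 = 0.178 per year (stated 0.356 and 0.176); HR 0.499.
- Probability of death with accrual A and follow-up F: 1 − [exp(−λF) − exp(−λ(A+F))]/(λA). With A = F = 2 this is 0.651 and 0.411. Expected deaths are 64 × (0.651 + 0.411) = 68.0 (stated 68).
- Power at 68 deaths and HR 0.499: 81.9% by Schoenfeld, 78.8% by Freedman (stated 80%).
- Number randomized: 128/0.94 = 136.2 (stated 136).

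The figures hold. The 8 patients between 128 and 136 are the subject of this point.

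**2. How many patients?** The planning allowance is 8/136 = 5.9%. At the cited 9/573 = 1.6%, it would be 0.016 × 136 ≈ 2. Neither is an observed count of non-starters in this trial.

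**3. Is the reason for exclusion valid?** Section 9.1 names two causes. Non-compliance does not make OS unanalyzable, because 6.2.2 defines OS by death from any cause and death can be recorded without treatment. True loss to follow-up does limit information, but 9.3 already censors patients lost to follow-up. Neither cause requires exclusion.

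**4. What could exclusion do to the test?** The assumptions are not in the protocol: no true difference, hazard 0.25 per year in both arms, 68 per arm, 2 years of accrual, 3 years of follow-up, unstratified log-rank test, 8 patients excluded, 8,000 simulated trials per row. Poor prognosis is modelled in two ways: non-starters drawn from the shorter-surviving half of their arm, or the very shortest survivors removed.

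| Split (experimental/standard) | Random non-starters | From shorter-surviving half | Shortest survivors |
|---|---|---|---|
| 4/4 | 4.9% | 5.0% | 5.9% |
| 6/2 | 4.8% | 6.1% | 8.8% |
| 8/0 | 5.0% | 9.8% | 14.9% |

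Entries are two-sided type I error in the treated set. In the 8/0 poor-prognosis cases nearly all of it is false benefit for the experimental arm (9.3 of 9.8 and 14.7 of 14.9 percentage points). By symmetry, 0/8 would do the reverse. The all-randomized test stayed between 4.5% and 5.2% throughout.

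**5. What does analysing everyone cost in power?** Take the pooled rate 0.1994 from 9.1 with HR 0.5, so hazards 2 × 0.1994/1.5 = 0.266 and 0.133, with 2 years of accrual and 3 years of follow-up. Expected deaths are about 68 with 64 per arm and about 72 with 68 per arm.

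- Treated set: Φ(√68 × 0.693/2 − 1.96) = 81.5%.
- All randomized, 4 non-starters per arm, experimental non-starters gaining nothing. Averaging log hazards, (64/68) × ln 0.5 = −0.652 (HR 0.52) and Φ(√72 × 0.652/2 − 1.96) = 79%. Averaging hazards, (64 × 0.5 + 4)/68 = 0.529, ln 0.529 = −0.636, and power is 77%.

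The cost is about 2 to 4 percentage points in this case. If the planned effect applied to non-starters too, power would rise slightly.

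**6. Would relabelling alone work?** No. A patient who never starts radiotherapy has no time origin under 9.3. Section 3.6 calls non-starters drop-outs and 9.3 censors dropouts at dropout, so they could be censored near day 0. The set would then be all-randomized in name but would add almost no deaths.

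**The case against.** The strongest reply is that the harm is hypothetical. Type I error stays at 5% if non-starting is random and reaches at most about 6% with a balanced split. Reaching 10-15% needs all 8 non-starters in one arm and poor survival among them, and the simulation selects on actual survival time, which is a strong form of dependence. No passage shows that non-starting depends on the arm, and the two plausible mechanisms could offset each other. The protocol regards 6% as a safety margin, and about 2 exclusions would matter less. The as-randomized analysis is prespecified, so readers would see both results.

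All of that stands, and it limits the point to lost protection, not shown bias. It does not repair the definition: the label is wrong and the unprotected set carries the confirmatory test.

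Three stronger readings should be resisted.

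- A reader might infer that the result will favour the experimental arm. The documents give no direction.
- A reader might take 13 of 141 (9.2%) from the synopsis as the exclusion rate. The body says 136 throughout, and the synopsis also differs on screening (658 against 322 in 9.1). This is a count to reconcile, not evidence of more exclusions.
- A reader might take an example with 10 experimental and 3 standard non-starters dying at the control rate, where the simulated HR is 0.50 in the treated set and 0.55 in all randomized, as a measure of bias. It shows dilution by untreated patients: the treated set returns the simulated effect.

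**Conclusion.** The point holds as a defect of definition in the confirmatory analysis. The set called ITT is a treated (modified ITT) set, consistently so in the synopsis, 3.6, 9.1 and 9.3, and its membership is settled after an open allocation. Non-compliance is not a valid ground for calling OS unanalyzable.

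The effect on the result cannot be sized from the protocol. It is nil if non-starting is unrelated to arm and prognosis. The 6-9% and 10-15% figures depend on the assumed 8 exclusions, unbalanced splits and poor survival among non-starters. The planned all-randomized analysis softens the problem but is not primary, and for patients who never start radiotherapy it has no defined time origin under 9.3. The safety-set and allocation-count mismatches are real but secondary.

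**What to change.** 1. In the synopsis, 3.6, 9.1 and 9.3, define ITT as all randomized patients analysed in the allocated arm, and make it the confirmatory population.
2. Rename the present set treated (modified ITT) and keep it as a sensitivity analysis.
3. Measure OS from randomization for everyone, reconciling the radiotherapy start date in 9.3 with 2.3 and 6.2.2.
4. Count deaths after stopping or never starting treatment. Censor only at the date last known alive, not at dropout from treatment.
5. Delete non-compliance from 9.1 as a reason for OS being unanalyzable.
6. Reconcile the safety set between the synopsis and 9.4, and the number allocated (141 or 136).

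**Cost.** No further patients are needed, and the all-randomized analysis is already planned. Items 3 and 4 are rule changes, not just wording, and vital status must be retrieved for the few non-starters. Some dilution is possible, about 2 to 4 points of power in the case above. Section 9.1 places this version at least 14 months after the last patient entered, so the number of non-starters can now be counted. The survival review described there was blinded, and 9.3 still has the full analysis plan to be written, so the change need not rest on results by arm.

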4. TRIAL DESIGN

This is a multicenter, randomized, open-label phase III trial for newly diagnosed glioblastoma patients with methylated MGMT promoter in their tumor. The study includes the following steps:

Screening phase (1-3 weeks after resection): Patients with previously untreated GBM are screened for the trial. After obtaining informed consent for determination of MGMT promoter methylation status and reference neuropathology, a block of paraffin-embedded tissue is sent for reference neuropathology review to the Department of Neuropathology, University of Bonn. From there, tissue is sent to MDxHealth, where the MGMT promoter methylation status is determined by methylation-specific PCR.

Baseline and randomization phase (week 3-5 after resection): Baseline examinations are performed. After obtaining the MGMT promoter status and confirmation of GBM histology (for the form to submit reference neuropathology and MGMT testing see appendix 3) and obtaining informed consent for trial participation, inclusion/exclusion criteria are evaluated and documented, patients are randomized for standard TMZ chemotherapy or experimental CCNU/TMZ therapy, both in combination with standard RT. Therapy (i.e. RT) has to start within 2 weeks after randomization and 5 weeks after surgery. A 5 week interval is generally accepted for clinical trials in GBM and does not impair therapeutic efficacy (Blumenthal et al., 2008).

Treatment phase: The treatment phase as well as the follow-up phase of the trial is summarized in figure 1. The treatment phase should start not later than 5 weeks after surgery and not later than 2 weeks after randomization and baseline visit.

[figure not shown]
The trial includes two treatment arms:

Experimental arm (CCNU/TMZ arm; 50% of patients): the first course of CCNU (100 mg/m² day 1) and TMZ (100 mg/m²/day, day 2-6) is started on the first day of RT (60 Gy in 2 Gy fractions, 5 days/week). The following 5 courses are applied 6 weeks after the start of the previous course. In the experimental arm, not more than 6 six week courses can be applied.

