Standard arm (TMZ arm; 50% of patients): the first application of TMZ is given on the first day of RT (60 Gy in 2 Gy fractions, 5 days/week). During RT, TMZ is given on a daily base with 75 mg/m²/day (including RT-free weekend days). RT with concomitant TMZ chemotherapy (6 weeks) is followed by a 4 weeks interval without therapy. In week 11 after the initiation of RT, the TMZ block chemotherapy ensues with 6 courses of TMZ 150-200 mg/m² day 1-5 of a 28 day course. It is recommended that TMZ chemotherapy is stopped after application of 6 courses (as suggested by Stupp et al., 2005).

Follow-up phase: After the end of the treatment phase, all patients will be followed by clinical examination and contrast-enhanced MRI every 12 weeks until 3 years after randomization. Follow-up of all patients ends 36 months after the inclusion of the last patient. All patients in the trial are followed until this time point.

Fig.1: Schematic overview of the study

* Laboratory and Clinical examinations, toxicity recording as detailed in table 1

- TMZ 75 mg/m² p.o./die over 6 weeks during RT
- TMZ 150 D200 mg/m² p.o. day 1 D5 of a 28 day course
- Radiotherapy of the tumor region, daily, 30 x 2 Gy
Total dose 60 Gy
- CCNU 100 mg/m² p.o. on day 1 +
TMZ 100 mg/m² p.o./die day 2 -6 of 42 day course

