5.2 Supply, package, storage and labelling of investigational products

CCNU and TMZ are both commercially available drugs approved for marketing authorization in Germany. Therefore the capsules are prescribed by the treating physician and provided by the local pharmacy. Drugs are to be kept in an appropriate, secure, locked area at the pharmacy of the participating center and are supplied on the day of intake by the pharmacy. CCNU will be taken by the patient in the hospital under supervision of study personnel. TMZ (day 2-6 of each course) is distributed by the trial center and taken on an outpatient base. The investigator, or a responsible party designated by the investigator, will maintain a careful record of the inventory and disposition of all drugs received using the Drug Accountability Record form. Since this is an open study and drugs are approved for marketing authorization no labelling will be performed. In this study CCNU is used in label. Temozolomide is only approved to be given in a monotherapy. Since in the experimental arm a combined therapy consisting of Lomustine + Temozolomide is provided, Temozolomide in the experimental arm is used off label. This combined therapy has been used before in a non-randomized clinical trial leading to an improved survival by acceptable toxicity ([name] et al 2006), thereby justifying the combination of both drugs and establishing the rational for this clinical trial (for details see chapter 1).

Temozolomide

TMZ is supplied in capsules of the following p.o. dosage strengths: 5 mg, 20 mg, 100 mg, 140 mg, 180 mg and 250 mg. Each capsule contains drug substance in combination with lactose, colloidal silicon dioxide, sodium starch glycolate, tartaric acid, and stearic acid. The capsule shells contain gelatin, titanium dioxide, and sodium lauryl sulfate. The capsules should be stored as indicated in the valid SmPC. Capsules are stable for at least 24 months when stored in amber glass bottles at this temperature. Patients are supplied with TMZ by the local investigator. TMZ as well as the combination of TMZ and CCNU are taken on an outpatient base. If vomiting occurs

during the course of treatment, no redosing of the patient is allowed before the next scheduled dose. The capsules should be taken on an empty stomach, therefore a minimum of 3 hours after a meal and with no food ingestion for 1 hour after TMZ and CCNU administration.

CCNU

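### The per-protocol set's two treatment requirements are met at different times (about day 48 versus day 75) while survival is counted from the start, so this secondary check carries a small timing bias

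*Protocol*

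**What the plan says.** The rule appears twice in the protocol. Section 9.3 states "The per-protocol analysis includes all patients who have received two courses of CCNU/TMZ in the experimental arm or concomitant TMZ" and continues "plus one course of adjuvant TMZ in the standard arm". The Synopsis (Statistical analysis) gives the same definition: "all patients who have received two courses of CCNU/TMZ (experimental arm) or concomitant TMZ plus one course of adjuvant TMZ (standard arm".

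The timing follows from the schedule:

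- **Experimental arm.** Section 4: "The following 5 courses are applied 6 weeks after the start of the previous course". CCNU is given on day 1 of a course, and Section 5.2 gives the rest: "TMZ (day 2-6 of each course) is distributed by the trial center".
- **Standard arm.** Section 4: "RT with concomitant TMZ chemotherapy (6 weeks) is followed by a 4 weeks interval without therapy", then "In week 11 after the initiation of RT, the TMZ block chemotherapy ensues with 6 courses of TMZ", dosed on days 1-5 of the course.

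Section 9.3 measures survival from the first day of radiotherapy. Sections 2.3 and 6.2.2 use randomisation instead. Either origin lies before the per-protocol requirement can be met. The protocol mentions no landmark and no delayed entry. The per-protocol comparison is additional to the confirmatory intention-to-treat analysis, but Section 9.3 expects the two to agree and repeats the survival analyses on this set.

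**The concern.** Membership depends on surviving long enough to receive the required treatment, and that time differs by arm. Take a patient treated on schedule who dies between day 48 and day 75. In the experimental arm the patient is in the set and the death counts. In the standard arm the patient is excluded and the death disappears. Because the clock starts before either requirement is met, the standard arm is credited with about 27 more days in which no death can be recorded.

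At stake is the reading of the consistency check. A set that tilts by construction can move away from the intention-to-treat result for reasons unrelated to adherence.

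**Working it through.** **1. The plan's own figure.** Inputs from Section 9.1: 64 per arm, death rates λ of 0.356 and 0.176 per patient-year, 2 years' recruitment, 2 years' follow-up in the original planning. With uniform accrual A and further follow-up F, P(death) = 1 − [exp(−λF) − exp(−λ(A+F))]/(λA). This gives 64 × 0.649 = 41.5 and 64 × 0.407 = 26.1, in total 67.6. The stated 68 events are reproduced, so the same model is used below.

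**2. Qualifying days (start of radiotherapy = day 1).**

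| Reading | Experimental | Standard | Gap |
|---|---|---|---|
| Last qualifying dose | 42 + 6 = day 48 | 42 + 28 + 5 = day 75 | 27 days |
| Full course length | 2 × 42 = day 84 | 42 + 28 + 28 = day 98 | 14 days |

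Section 5.1.4 allows the adjuvant phase to start within 5 days either side of 4 weeks after the last radiotherapy day. If that day is day 40 (assumed Monday start), the standard arm's last dose lies between days 67 and 77.

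**3. Standard-arm deaths removed without a counterpart.** 64 × [exp(−λ·48/365.25) − exp(−λ·75/365.25)]:

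- λ = 0.356 (planned): 64 × (0.9543 − 0.9295) = 1.6
- λ = 0.1994 (blinded pooled rate, Section 9.1): 64 × (0.9741 − 0.9599) = 0.9

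**4. Shift when there is no true effect.** Among patients alive at day L, let q be the probability of dying within follow-up. Expected follow-up after L is q/λ per patient, so the event rate counted from day 1 is q/(L + q/λ) = λ/(1 + λL/q). The apparent hazard ratio (experimental to standard) is therefore (1 + λL_std/q_std)/(1 + λL_exp/q_exp). Here q = 1 − m·exp(λL), where m = [exp(−3λ) − exp(−5λ)]/(2λ) for 2 years' recruitment and 3 years' follow-up; L is in years.

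- λ = 0.1994, m = 0.4534: (1 + 0.0409/0.5277)/(1 + 0.0262/0.5346) = 1.0776/1.0490 = 1.027
- λ = 0.356, m = 0.2459: (1 + 0.0731/0.7355)/(1 + 0.0468/0.7424) = 1.0994/1.0630 = 1.034
- Full-course reading: 1.1026/1.0873 = 1.014 and 1.1309/1.1117 = 1.017

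A simulated Cox model (400,000 per arm, λ = 0.1994) gave 1.026 with days 75/48 and 0.999 with day 75 in both arms. On the planned rates it gave about 0.508 for the per-protocol set against about 0.494 for all patients.

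**5. Size against random error.** With 68 events the standard error of the log hazard ratio is about 2/√68 = 0.243. ln(1.026)/0.243 = 0.11 and ln(0.508/0.494)/0.243 = 0.12.

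**6. Small-sample behaviour (log-rank, 64 per arm, 10,000 runs, deaths only).**

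- No effect, λ = 0.356: false significance 3.6% favouring standard and 1.5% favouring experimental (nominal 2.5% each).
- No effect, λ = 0.1994: 3.0% and 1.9%.
- Planned rates: power 88% in all patients, 83% with days 75/48, 86% with day 75 in both arms.

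**7. Delay of course 2.** Using the formula in step 4 at λ = 0.1994: a 2-week delay (last dose day 62) gives 1.0776/1.0637 = 1.013. A 6-week delay (48 + 42 = day 90) gives 1.0776/1.0938 = 0.985. The direction turns once the delay exceeds 75 − 48 = 27 days.

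**The case against.** **The effect is negligible.** About a tenth of a standard error will not make two analyses look inconsistent. Even that may be too high: constant hazard from day 1 sits badly with eligibility that requires a life expectancy of at least 12 weeks (84 days, beyond day 75) and a Karnofsky score of at least 70%. This stands, and it sets the weight of the point.

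**The direction is not fixed.** Section 1.4.2 places CCNU myelosuppression mainly at 4-6 weeks, just when course 2 falls due. Section 1.1 reports 42% high-grade myelotoxicity in the phase II trial, and Section 5.1.3 assumes treatment failure only for a delay of more than 6 weeks. Long delays reverse the sign, and exclusions for toxicity are a separate selection whose direction the documents do not settle. This also stands. It limits any claim about direction but does not defend unequal time requirements.

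**The rule is matched on exposure.** Each arm needs its radiotherapy-phase chemotherapy plus one later course. That is a reasonable concept of adherence. The fault lies in starting the clock before the concept can be met.

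**A later plan could settle it.** Section 9.3 defers the full analysis to a later plan. But the set and the time origin are already fixed in the protocol, and a plan that follows them keeps the bias.

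**A stronger reading through progression.** A reader might add progression in the gap, using the 7.9-month median PFS in Section 1.1: 1 − exp(−ln 2/7.9 × 27/30.44) = 7.5%, or 4.8 of 64. The documents do not support this. The first scheduled MRI is 12 weeks after randomisation, and radiotherapy starts within 2 weeks of randomisation, so the scan falls at about radiotherapy day 70 to 84, give or take 5 days. Until 12 weeks after radiotherapy, Section 6.2.1 accepts progression only with new enhancement outside the field or histological proof. Therapy continues until the reference neuroradiologist confirms it. Almost nobody can leave the set through progression in that window, and the 7.9 months are not specific to MGMT-methylated patients.

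**Conclusion.** The point holds as a small timing bias in a secondary analysis. As scheduled, the per-protocol rule guarantees survival to about day 48 in one arm and day 75 in the other. On deaths alone this removes about 0.9 to 1.6 of 64 standard-arm patients and moves a null hazard ratio to about 1.03 (1.01 to 1.02 on the full-course reading) against the experimental arm.

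This assumes constant hazard, on-schedule dosing and no other selection. The 12-week life-expectancy criterion probably makes it smaller, and delays of course 2 beyond about 27 days reverse it for the patients concerned.

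Two further inferences would go too far. The primary intention-to-treat result is not affected, because that set requires only a first dose of chemotherapy. Nor can the per-protocol result be said to favour the standard arm whatever the delays. The case for acting is that the protocol names this set as its consistency check and the correction is cheap.

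**What to change.** Keep the treatment requirement. In the per-protocol OS and PFS analyses, let each patient enter the risk set only on the date of the last qualifying dose (delayed entry). A death at a time when only one arm is at risk then carries no weight in the log-rank or Cox comparison, so the day 48-75 asymmetry disappears; in a deaths-only simulation with no true effect, delayed entry returned a hazard ratio of 1.00.

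The alternative is one common landmark in both arms, with time measured from it. Day 75 is too early: compliant standard-arm patients may take their last qualifying dose up to about day 77 within the permitted window. Day 98 after the start of radiotherapy covers that and a 6-week delay of experimental course 2 (day 90). It would not cover a comparable 6-week delay of the first adjuvant course (75 + 42 = day 117), which makes delayed entry the tidier choice.

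State whether receiving a course means the last dose or the full course length. Report the present from-start version only as a sensitivity analysis.

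The cost is a few sentences and a few lines of code. A few early events leave the per-protocol analysis and precision falls slightly. Neither option removes selection by toxicity, which should be acknowledged.
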